4.11.4.1 Hematology, Clinical Chemistry, and Coagulation

The following by treatment summaries will be generated separately for hematology, clinical chemistry, and coagulation laboratory tests:

- Frequency table for newly occurring on-treatment Grades 3 or 4.
- Shift tables using DAIDS grades to compare baseline to the worst on-treatment value.
- For laboratory tests where DAIDS grades are not defined, shift tables using the low/normal/high classification to compare baseline to the worst on-treatment value.
- Listing of all laboratory data with values flagged to show the corresponding DAIDS grades and the classifications relative to the laboratory normal ranges.

4.11.4.2 Biomarkers

Blood samples will be collected from all subjects for exploratory biomarker research at the time specified in the SoA where local regulations allow.

The following will be monitored:

- C-reactive protein (CRP)
- Testosterone
- Ferritin
- D-dimer
- Procalcitonin
- Troponin

The by visit biomarker data will be summarized by treatment group for the Safety set. Biomarker data over time will also be plotted for each biomarker type.

4.11.4.3 Pharmacokinetics

PK analysis will be performed on the PK set.

Samples will be collected at pre-dose and 2h post first dose, and at pre-dose on Day 3, 7 and 14, from at least 200 subjects who receive intervention and have evaluable PK.

PK concentrations of GT0918 (and any relevant metabolites such as GT0955) will be summarized by time point using descriptive statistics for GT0918 treatment group. All PK concentration data will be listed as appropriate.

All concentrations below the LLOQ will be displayed in listings as zero with a flag and handled as zero in any calculations of summary statistics, but handled as missing for the calculation of the geometric means and their CV. Any missing PK parameter data will not be imputed.

4.11.5 Vital Signs, Physical Findings and Other Observations Related to Safety

Vital Signs

Vital signs include:

- Height and weight at screening only
- Body temperature
- Systolic blood pressure (BP), diastolic BP
- Pulse rate
- Respiration rate
- Saturation of peripheral oxygen
- Supplemental oxygen flow rate, FiO_2 if known, and method of delivery, if applicable or clinical indicated
- Additional vital signs if applicable or clinical indicated

The observed Vital Signs value and change from baseline to each post-baseline time point will be summarized using descriptive statistics.

A by-subject listing of vital sign parameters will be provided.

Physical Findings

Full physical exam should be done at screening visit. For the subsequent visits, symptom directed physical exam can be done per investigator's discretion.

A by-subject listings of physical examination results will be provided.

ECG

A 12-lead ECG can be done per investigator's discretion. All ECG findings including interpretation and clinically significant status will be listed by subject.

Chest X-ray and CT-scan

Chest X-ray or CT-Scan can be done per investigator's discretion. The results will be listed by subject if any.

Pregnancy Test

Pregnancy test results at Day 28 visit will be listed by subject.

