#### **10.7.4 Other safety data**

##### **10.7.4.1 Vital signs**

- Shift table from baseline to worst on-treatment result.
- Table with descriptive statistics at baseline, one or several post-baseline time points and change from baseline to this/these post-baseline time points.

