**Severe COVID-19**

- Positive testing by standard RT-PCR assay or an equivalent test
- Symptoms suggestive of severe systemic illness with COVID-19, which could include any symptom of moderate illness or shortness of breath at rest, or respiratory distress
- Clinical signs indicative of severe systemic illness with COVID-19, such as respiratory rate  $\geq 30$  per minute, heart rate  $\geq 125$  per minute,  $\text{SpO}_2 \leq 93\%$  on room air at sea level or  $\text{PaO}_2/\text{FiO}_2 < 300$
- No criteria for Critical Severity

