Continuous data will be summarized in terms of the mean, standard deviation (SD), median, minimum, maximum, and number of observations, unless otherwise stated. Continuous data that are expected to be skewed will be presented in terms of the maximum, upper quartile, median, lower quartile, minimum and number of observations. The minimum and maximum will be reported to the same number of decimal places as the raw data recorded in the database. The mean, median, lower quartile and upper quartile will be reported to one more decimal place than the raw data recorded in the database. The SD will be reported to two more decimal places than the raw data recorded in the database. In general, the maximum number of decimal places reported shall be four for any summary statistic.

Categorical data will be summarized in terms of the number of subjects providing data at the relevant time point (n), frequency counts and percentages. Any planned collapsing of categories will be detailed in the SAP text and the data displays.

Percentages will be presented to one decimal place. Percentages will not be presented for zero counts. Percentages will be calculated using n as the denominator. If sample sizes are small, the data displays will show the percentages, but any textual report will describe frequencies only.

Changes from baseline in categorical data will be summarized using shift tables where appropriate.

P-values greater than or equal to 0.0001, in general, will be presented to four decimal places. P-values less than 0.0001 will be presented as “<0.0001” and p-values greater than 0.9999 will be presented as “>0.9999”.

Confidence intervals will be presented to one more decimal place than the raw data.

Analysis Visit Window:

For unscheduled visits, analysis visit windows will be applied as in [Table](#) below. Analysis visit windows are only used for by visit summaries, not for time to event calculation which will be based on actual date of data collected.

Table 1 Analysis Visit Window for Unscheduled Visits of blood samples

Mapped to	Visit Window
Screening	[Day -1, Day 1]
Day 3	[Day 2, Day 4]
Day 7	[Day 6, Day 8]
Day 14	[Day 13, Day 15]
Day 28	[Day 26, Day 30]
Day 42	[Day 40, Day 44]

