4.11 Safety Evaluation

All safety analyses will be based upon the Safety set. All listings and tables will be presented by treatment group.

The overall observation period will be divided into 5 segments:

1. pre-treatment period: from day of patient's informed consent to the day before first dose of study medication
2. on-treatment period: from the day of first dose of study drug (D1) to the day of last dose (up to D14).
3. post-treatment period: from the day after last dose (up to D15) to D28.
4. treatment and post-treatment period: from D1 to D28.
5. safety follow up period: from D29 to D42.

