4.11.3 Deaths, Serious Adverse Events, and Other Significant Adverse Events

SAE

An SAE is defined as one of the following:

- Is fatal
- Is life-threatening
- Results inpatient hospitalization or prolongation of existing hospitalization
- Results in a persistent or significant disability/incapacity
- Constitutes a congenital anomaly/birth defect
- Is medically significant, i.e., defined as an event that jeopardizes the patient or may require medical or surgical intervention to prevent one of the outcomes listed above
- Note that hospitalizations for the following reasons should not be reported as SAEs:
 - Routine treatment or monitoring of the studied indication, not associated with any deterioration in condition.
 - Elective or pre-planned treatment for a pre-existing condition that is unrelated to the indication under study and has not worsened since signing the informed consent.

- Social reasons and respite care in the absence of any deterioration in the patient's general condition.
- Note that treatment on an emergency outpatient basis that does not result in hospital admission and involves an event not fulfilling any of the definitions of a SAE given above is not an SAE.

AE Summaries by System Organ Class and Preferred Term

The incidence for the following will be summarized by SOC and PT, unless otherwise specify:

- SAEs
- SAEs Related to Study Drug
- SAEs with Outcome Fatal
- TEAEs Leading to Study Drug Discontinuation

Separate tables for on-treatment period and safety follow up period will be provided, and below by-subject listings will be provided:

- All SAEs
- All Fatal SAEs
- All AEs leading to Study Drug Discontinuation

Adverse Events of Special Interest (AESI)

Adverse events of special interest to be monitored include gastrointestinal, cardiovascular, hepatic, and neurological adverse events (dizziness, headache), hematological (anemia, leukopenia, neutropenia) and elevated creatinine kinase. (Appendix 6.5)

TEAEs of special interest will be summarized by SOC and PT.

Time to TEAEs of Special Interest

Time to TEAEs of special interest (in days) is defined as:

First date when TEAEs of special interest onset - first dosing date + 1.

If a patient has not experienced TEAEs of special interest by completion or early discontinuation of study/study treatment, the patient will be censored at the date of their last visit.

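### SAP 4.11.5 omits, without explanation, the protocol's baseline-to-worst vital-sign shift table, leaving no by-arm count of subjects whose pulse, respiratory rate or blood pressure worsened

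*SAP*

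**What the plan says.** Protocol 10.7.4.1 lists two outputs for vital signs. One counts movement between categories: "Shift table from baseline to worst on-treatment result". The other summarizes levels and changes for the group: "Table with descriptive statistics at baseline, one or several post-baseline time points and change from baseline to this/these post-baseline time points".

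SAP 4.11.5 also has two. For the summary it says: "The observed Vital Signs value and change from baseline to each post-baseline time point will be summarized using descriptive statistics". For individual data it says: "A by-subject listing of vital sign parameters will be provided". It mentions neither a shift table nor a worst on-treatment value.

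The SAP's general conventions (4.2) define the descriptive statistics: "Continuous data will be summarized in terms of the mean, standard deviation (SD), median, minimum, maximum, and number of observations, unless otherwise stated". For safety outputs SAP 4.11 adds: "All listings and tables will be presented by treatment group".

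Protocol 10.1 describes the SAP as complementing the protocol and taking precedence where the two differ.

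**The concern.** A shift table from baseline to worst value answers a question that a by-visit summary does not: how many subjects in each arm moved from an acceptable value to an abnormal one at any time on treatment. Harm in pulse, respiratory rate or blood pressure may affect a minority, at different visits in different subjects. The mean at each visit then changes little.

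This matters somewhat more here because cardiovascular events and dizziness are among the adverse events of special interest (SAP 4.11.3), while ECGs are done only at the investigator's discretion and are only listed (SAP 4.11.5). Pulse and blood pressure are therefore the main cardiovascular measures taken on a schedule. At stake is the completeness of the safety report. No efficacy endpoint, alpha level or primary conclusion is involved.

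**Working it through.** The plan states no figure on this point, so there is none to reproduce. The check is a comparison of texts, followed by an illustration with assumed inputs.

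**1. The two documents side by side**

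| Output | Protocol 10.7.4.1 | SAP 4.11.5 |
|---|---|---|
| Shift, baseline to worst on-treatment | Planned | Absent |
| Descriptive statistics with change from baseline | Planned | Planned |
| By-subject listing | Not named in this section | Planned |

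One of the two protocol outputs is dropped and a listing is added.

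**2. Does another SAP rule bring the table back?** SAP 4.2 calls for shift tables, where appropriate, for categorical data. The SAP defines no categories for vital signs, so the rule has nothing to act on. By contrast, SAP 4.11.4.1 keeps baseline-to-worst shift tables for laboratory tests and names their categories (DAIDS grades, or low/normal/high).

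**3. Is a reason given?** The SAP revision history itemises several removed analyses, and this table is not among them. SAP 4.10.1.1.3, which explains a change from the protocol, covers only missing primary assessments.

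**4. What do the remaining outputs count?** The mean, SD and median describe the group at one visit. The minimum and maximum give one extreme per arm and visit. The listing gives every value but no total. None of them counts, by arm, the subjects who worsened.

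**5. How much can a by-visit mean hide?** Inputs: 334 per arm (668 randomized 1:1, from protocol 10.9). Assumed, because the documents give no figures: SD of the change 10 or 15 units; a share f of one arm (2%, 5% or 10%) worsening by d = 20 or 30 units at a visit; everyone else unchanged on average.

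- Shift in the arm mean = f × d
- SE of the between-arm difference = SD × √(2/334), which is 10 × 0.0774 = 0.77 or 15 × 0.0774 = 1.16

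| f (subjects of 334) | d | Mean shift | Shift in SEs, SD 10 | Shift in SEs, SD 15 |
|---|---|---|---|---|
| 2% (7) | 20 | 0.4 | 0.52 | 0.34 |
| 2% (7) | 30 | 0.6 | 0.78 | 0.52 |
| 5% (17) | 20 | 1.0 | 1.29 | 0.86 |
| 5% (17) | 30 | 1.5 | 1.94 | 1.29 |
| 10% (33) | 20 | 2.0 | 2.58 | 1.72 |
| 10% (33) | 30 | 3.0 | 3.88 | 2.58 |

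At 2% to 5% affected, the shift stays below 2 SEs throughout. At 10% it exceeds 2 SEs in three of the four cases, so a larger affected group would usually show in the means. The calculation puts all deterioration at one visit. If the same subjects worsened at different visits, each visit's mean would move less.

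**The case against.** The strongest reply is that silence is not a difference. The SAP complements the protocol, nowhere cancels the table, and does not list it among its removals. That is arguable, but it does not settle the matter. SAP 1 says the document describes the analyses for the study report, and someone programming from 4.11.5 would not produce the table. The revision history compares SAP versions, not the SAP with the protocol. On either reading the text needs a correction.

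Four stronger readings are tempting, and the documents do not support them.

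- *A reader might infer that the SAP swapped the shift table for means and changes.* The descriptive table was already in the protocol beside the shift table, and its statistics include the SD, median, minimum and maximum.
- *A reader might infer that individual deterioration becomes invisible.* The by-subject listing shows it, and protocol 7.2.2 has investigators report clinically significant vital signs in the eCRF. What is missing is a count.
- *A reader might infer that respiratory deterioration goes uncounted because protocol 8.1.2 exempts COVID-19 hypoxemia from AE reporting.* The exemption covers hypoxemia requiring oxygen or ventilation, unless the investigator considers it related to study drug. Oxygen need is counted by arm elsewhere: in the separately summarized components of the primary endpoint (SAP 4.10.2), and in the NIAID scale categories and the summary of new oxygen use (SAP 4.10.3).
- *A reader might infer that a restored table would expose a stark contrast, such as ten subjects with a 40-beat rise on one arm and none on the other.* That needs a category that isolates such a rise. Protocol Appendix 3 gives heart-rate limits of 90 and 125. A subject starting below 85 (125 − 40) stays under 125 after a 40-beat rise, and ordinary variation would carry subjects on both arms across 90.

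Two further limits stand. Footnote 7 of the Schedule of Activities names SpO2 for the screening visit, whereas protocol 7.2.2.2 and SAP 4.11.5 list it without that limit, so post-baseline SpO2 may be sparse whichever table is used. Visits may also be held by telephone, so some vital signs may be missing.

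**Conclusion.** The point holds in a limited form. The SAP leaves out one of two vital-sign outputs that the protocol commits to and gives no reason. The outputs that remain give no by-arm count of subjects whose pulse, respiratory rate or blood pressure worsened.

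The omission itself is read directly from the text. Its practical weight rests on the assumed SDs, shares and sizes of change above: under them, means miss an affected minority of about 2% to 5% and usually reveal one of 10%. Nothing in the documents says that such a minority exists. This is a low-severity, low-cost correction to safety reporting.

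**What to change.** Restore the shift table from baseline to worst on-treatment value in SAP 4.11.5, by arm on the Safety set, using the SAP's definitions of baseline (4.2) and on-treatment period (4.11). Fix low/normal/high reporting categories for each vital sign before unblinding, since neither document defines any for this table.

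Appendix 3 can inform the upper categories for respiratory rate and heart rate. It is a classification of disease severity, however. It has no low limits for these two signs and nothing for temperature, and it gives blood-pressure limits only under shock. The sponsor must therefore define the rest, as reporting categories only. The SpO2 entry in footnote 7 should be reconciled with protocol 7.2.2.2 and SAP 4.11.5, so that it is clear what post-baseline data the table can use.

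If the sponsor intends to drop the table, the SAP should say so and give the reason. The cost is a few lines of SAP text and one more table from data already collected. No visit, assessment or treatment rule changes.

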4.11.6 Independent Data Monitoring Committee (IDMC)

An IDMC will be responsible for monitoring and reviewing the clinical study data for safety and efficacy during the study prior to the final data analysis. The primary goal of the IDMC is to review the interim results regarding the continuing safety of study subjects and the continuing validity and scientific merit of the study. An IDMC will review the interim analysis report to conclude early efficacy, make recommendations about early study closure, change study population, or change to study sample size. More details please refer to section 4.11.2.1. Rigorous steps will be taken (e.g., firewalls) where possible to minimize the information that can be inferred by observers.

4.12 Determination of Sample Size

The primary endpoint event rate for the treatment arm is assumed at 97% and for the placebo arm is assumed at 91%.

The sample size was calculated using EAST v6.5 software for a group sequential test for 2 proportions. With a total of 668 subjects the study will have about 90% power at a one-sided 0.025 significance level of the hospitalization or death rate using a Chi-square test with one interim analysis at 50% of the information (when 334 subjects have been observed for 28 days).

5 REFERENCES

- [1] SAS® Version 9.4 of the SAS System for Personal Computers. Copyright © 2002-2003. SAS Institute Inc. SAS and all other SAS Institute Inc. product or service names are registered trademarks or trademarks of SAS Institute Inc., Cary, NC, USA.
- [2] Division of AIDS (DAIDS) Table for Grading the Severity of Adult and Pediatric DAIDS Adverse Event Grading Tables | DAIDS Regulatory Support Center (RSC) (nih.gov)

6 APPENDICES**6.1 Schedule of Assessments (SoA)**

Table 4 Schedule of Activities

-	Screen	Treatment Period					Early Withdrawal ¹⁹	Post-treatment		Safety Follow Up ²⁰
Study Day (Visit Window ± days)	D-1	D1	D3	D7 (±1)	D14 (+1)		(+2)	D15	D28 (±2)	D42 Phone Call (±2)
Informed Consent	X									
Inclusion/Exclusion Review¹	X									
Demographics²	X									
Preexisting Conditions and Medical History³	X									
NIAID Ordinal Scale⁴	X	Daily								
Prior Treatment⁵	X									
Tobacco Use	X									
Physical Examination⁶	X	Symptom Directed PE only if Clinical Indicated								
Vital Signs⁷	X		X	X	X	X			X	
Nasopharyngeal swabs⁸	X		X	X	X	X			X	
Randomization⁹	X	X								
Hematology¹⁰	X			X	X	X			X	
Chemistry¹⁰	X			X	X	X			X	
Biomarkers¹⁰	X		X		X	X			X	
Coagulation¹⁰	X				X	X			X	

Drugs and Diary Dispense¹¹	X	X							
GT0918 or Placebo Administration¹¹			Daily from D1 to D14						
Subject Diary¹¹	X		Daily from D1 to D14						
Questionnaire (Symptoms; Overall Clinical Status;)¹¹					Daily				
Chest X-ray or CT Scan¹²					Clinically Indicated				
12-ECG¹²					Clinically Indicated				
Hospitalization events¹³						Daily			
Clinical status and concomitant procedures if subject is hospitalized¹⁴						Daily if hospitalized			
Adverse Events¹⁵							X		
Concomitant Medications¹⁶							X		
Pharmacokinetics¹⁷		X	X	X	X				
Pregnancy test¹⁸	X							X	
COVID-19 vaccination status	X								

Annotation:

1. Inclusion/Exclusion review: every subject needs to meet all inclusion and exclusion criteria. The eligibility checklist needs to be signed by the investigator or sub-investigator.
2. Demographics: includes age, gender, race, and ethnicity.
3. Pre-existing conditions and medical history: obtained from interview or available information and including timing of exposure and onset of symptoms suggestive of SARS-CoV-2 infection.
4. NIAID ordinal scale to be completed daily through Day 28 or 14 days after last dose. This information can be collected from questionnaire; reported events; or directly from the patient.
5. Prior treatments within last 30 days.
6. Physical exam (PE): Full physical exam should be done at screening visit. For the subsequent visits, symptom directed PE can be done per investigator's discretion. If the result is clinically significant, the PE result should be recorded in eCRF.
7. Vital sign: documentation of hospital-based exam is acceptable. Vital signs include body temperature, pulse rate, systolic and diastolic blood pressure, respiratory rate. For screening visit, SpO₂, and supplemental oxygen flow rate, FiO₂ if known and method of delivery if applicable, also need to be recorded. Record blood pressure and SpO₂ while subject is at rest.
8. Nasopharyngeal (NP) swabs: Only NP swab sample is acceptable. The method of taking samples should be consistent for each subject during the whole period of this study. This does not need to be the same before screening visit, when the subject is first time confirmed SARS-CoV-2 positive at local laboratory and/or Point of

Care testing. Sample for first positive test must be collected within 3 days prior to start of dosing. Local laboratory and/or Point of Care testing are acceptable.

9. Randomization: randomization should be via the Interactive Voice/Web (IxRS) Response System. Randomization should be done after confirmation the subject meets all inclusion/exclusion criteria. Drugs and Diary Dispense should occur after randomization. It is allowed for the subject to take the drug on the same day of the screening visit after confirmation of eligibility and randomization (the screening visit is counted as D1 too). The Subject Diary should start to be completed.

10. Laboratory tests: Hematology, Chemistry (including Creatinine Kinase), Biomarkers (including Procalcitonin, C-reactive protein, D-dimer, Ferritin, Troponin, Testosterone), Coagulation. For details refer to Section 7.2.2 and 7.2.4.

11. GT0918 or placebo administration: GT0918 or placebo will be given orally once daily on Days 1-14 during the study period after a meal (± 2 hours for medication scheduling). The drug taken time should be recorded with subject diary. If the screening day is also D1, the subject does not need to follow the drug taken window on screening day/D1. For details refer to Section 6.1.

Subject Diary should be completed every day since screening visit until D14 or the last dose.

Questionnaire should be completed every day since screening visit to the end of post-treatment. For details refer to Section 7.2.6.

12. Chest X-ray or CT-Scan or 12-ECG can be done per investigator's discretion. If investigator deems the result is clinically significant, the result should be recorded with eCRF.

13. Hospitalization events: if the subject is hospitalized, the treatment may be continued to the 14 days per PI. Hospitalization is defined as ≥ 24 hours in hospital of care. For details refer to Section 7.1.2.

Record if the following events occur:

- Emergency room visits
- Hospitalized
- ICU admittance
- Extended care facility admittance
- Discharge

14. Documentation from hospital records is acceptable.

Includes:

- Limitation on activities due to COVID-19
- Ongoing hospital medical care
- Supplemental oxygen
- Non-invasive ventilation or high flow oxygen device
- Mechanical ventilation
- ECMO, or

15. Adverse events: any events that occur after signing the informed consent are considered AEs as defined in Section 10.3.

16. Concomitant medications: all medications administered within 30 days prior to the first dose of study treatment through 30 days after the last dose of study treatment will be recorded in the concomitant medications, for details refer to Section 6.4.

17. Pharmacokinetics (PK) samples only need to be taken for at least 200 subjects, who will be assigned according. For details refer to Section 7.2.3.

18. All women regardless of childbearing potential must complete a serum pregnancy test at screening visit, urinary pregnancy test on day 28 as per the schedule of assessment for women of childbearing potential. Local laboratories will be used for the analysis of serum and urinary pregnancy tests.

19. Early withdrawal (EW): if the subject is early withdrawn from this study for any reason (Section 7.1.4), the subject should complete the EW visit, and the visit should occur within 2 days of the EW day. The subject will go to the safety follow-up period for additional 28 days after his last dose.

20. D42 (or 28 days ± 2 post last dose if subject is withdrawn early) safety follow-up visit is phone call visit.

